Note 1: For subjects diagnosed with a neurological event (e.g., stroke, TIA), mRS and NIHSS should be performed after the event. It is recommended that the subject be contacted regarding an mRS assessment at 90±14 days following any suspected stroke; the simplified mRS questionnaire may be used for this follow-up assessment and may be collected by telephone. It is also recommended that imaging be performed after the event to screen for DRT. If performed, imaging results should be sent to the core laboratory.

- All antiplatelet medications, which should be administered in accordance with local standard of care. Subjects must be treated with SAPT (aspirin or P2Y₁₂ inhibitor) for at least 3 months following WATCHMAN FLX implantation.
- Physical assessment as per local standard of care
- Biochemical markers including measures of coagulation, platelet and endothelial activation and inflammation. TEE is required for all subjects who have a WATCHMAN FLX™ LAA Closure Device implanted in the correct position at 45 days and should be performed per the core lab guidelines, including assessment of device seal and device surface morphology (inclusive of tissue coverage) post implant procedure. Results must be sent to the core lab for independent analysis.
- TEE is optional at 3 months for subjects who have a WATCHMAN FLX™ LAA Closure Device implanted in the correct position if there is no leak at 45 days. However, if TEE is performed results must be sent to the core lab for independent analysis.
- CT is required for all subjects who have a WATCHMAN FLX™ LAA Closure Device implanted in the correct position and should be performed per the core lab guidelines, including assessment of device seal, device-related thrombus (including HAT) and device surface morphology (inclusive of tissue coverage) post implant procedure. Results must be sent to the core lab for independent analysis.
- Cardiac MRI assessment, including 4D cardiac MRI flow analysis of the LA and LAA, is optional but if performed, the results must be sent to the core lab for independent analysis.

Subjects who are enrolled but not implanted with a WATCHMAN FLX device in the correct position during the index procedure will be followed for safety through 12 months after the initial attempted index procedure but will not undergo imaging assessments or evaluation of biochemical markers including measures of coagulation, platelet and endothelial activation and inflammation.

10.8.3. 12-Months Follow-up (365±30 Days)

All subjects successfully implanted with a WATCHMAN FLX device will be evaluated at 12 months after the index procedure. The study eCRFs identify the specific data points to be collected as listed below.

- Complete safety event assessment, including any SAE, ADE, SADE, USADE, device deficiency with associated treatment, and any CEC event regardless of seriousness and device relationship.

Note 1: For subjects diagnosed with a neurological event (e.g., stroke, TIA), mRS and NIHSS should be performed after the event. It is recommended that the subject be contacted regarding an mRS assessment at 90 ± 14 days following any suspected stroke; the simplified mRS questionnaire may be used for this follow-up assessment and may be collected by telephone. It is also recommended that imaging be performed after the event to screen for DRT. If performed, imaging results should be sent to the core laboratory.

- All antiplatelet and other cardiovascular medications should be administered in accordance with local standard of care.

10.9. *Study Completion*

All enrolled subjects will be followed for the duration of 12 months post procedure. A subject's participation in the study will be considered complete after the 12-month follow-up visit. Subjects who are enrolled but not implanted with a WATCHMAN FLX device in the correct position during the index procedure will be followed for safety through 12 months after the initial attempted index procedure but will not undergo imaging assessments or evaluation of biochemical markers including measures of coagulation, platelet and endothelial activation and inflammation.

10.10. *Source Documents*

It is preferable that original source documents, when available, are maintained at the investigative center. In lieu of original source documents, certified copies are required to be maintained. A certified copy is a copy (irrespective of the type of media used) of the original record that has been verified (i.e., by a dated signature or by generation through a validated process) to have the same information, including data that describe the context, content, and structure, as the original. Source documentation includes but is not limited to those items

noted in **Table 10.10-1**. Source documentation provided to the Sponsor for assessment/adjudication will be deidentified per local law and regulations.

Table 10.10-1: Source Documentation Requirements

Requirement	Disposition
Printed, optical, or electronic document containing source data. Examples may include but are not limited to the following: hospital records; laboratory notes; device accountability records; photographic negatives; radiographs; records kept at the investigation center, at the laboratories and at the medico-technical departments involved in the clinical investigation.	Retain at center

Note 1: Please see **Table 23.2-1** for definitions of “source data” and “source document.”

11. Statistical Considerations

11.1. *Endpoints*

Procedural and post-procedure information will be collected as detailed in the clinical study schedule (**Table 10.1-1**) and will be summarized using descriptive statistics for continuous variables (e.g., mean, standard deviation, n, minimum, maximum) and frequency tables or proportions for discrete variables. The Kaplan-Meier product-limit method will be used to estimate rates for time-to-event endpoints. Adverse event and SAE rates will be reported.

11.2. *General Statistical Methods*

All statistical analyses will be performed using the SAS System software, version 9.2 or later (Copyright[©] 2000 SAS Institute Inc., SAS Campus Drive, Cary, North Carolina 27513, USA. All rights reserved).

All statistical analyses will be conducted according to applicable Standard Operating Procedures, Work Instructions, and the study-specific statistical analysis plan.

Statistical models that account for censored data will be employed in appropriate circumstances (e.g., for time-to-event outcomes).

11.2.1. *Analysis Sets*

Endpoints will be analyzed on an intention-to-treat (ITT) basis and an implanted basis. For ITT analyses, all subjects who sign the IEC-approved study ICF (see Section 10.3) and are enrolled (see Section 9.1) in the study will be included in the analysis, whether or not a study device was implanted. For implanted analyses, ITT subjects who had the study device implanted in the correct position during the index procedure will be included in the analysis.

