9.1. Point of Enrollment

A subject is considered enrolled in the study when the subject or the subject's legally authorized representative signs an ICF approved by the IEC. No study-specific tests, procedures, etc. can take place until the ICF is signed. A subject who is determined to not meet study specific clinical eligibility criteria after signing consent will be considered a screen failure (see **Table 9.5-1**) and will not count towards the enrollment ceiling.

9.2. *Withdrawal*

All subjects enrolled in the clinical study (including those withdrawn from the clinical study) shall be accounted for and documented. If a subject withdraws from the clinical investigation the reason(s) shall be reported. Reasons for withdrawal include but are not limited to physician discretion, subject choice to withdraw consent, or death. Reasons for study exit will be captured in the secure electronic data capture (EDC) system. If such withdrawal is due to problems related to device safety or performance, the investigator shall ask for the subject's permission to follow his/her status/condition outside of the clinical study.

While all efforts will be made to minimize attrition, subjects may withdraw from the study at any time, with or without reason, and without prejudice to further treatment. Withdrawn subjects will not undergo any additional study follow-up, nor will they be replaced. The investigator may discontinue a subject from participation in the study if the investigator feels that the subject can no longer fully comply with the requirements of the study or if any of the study procedures are deemed potentially harmful to the subject. Data that have already been collected on withdrawn subjects will be retained and may be used for analysis unless local regulations apply. No new data will be collected after subject withdrawal.

All applicable case report forms up to the point of subject withdrawal and an "End of Study" form for the subject must be completed. If the withdrawal is due to investigator discretion, the investigator should follow-up with the subject per standard of care.

9.3. *Lost to Follow-Up*

All enrolled subjects will be followed for up to 12 months post-procedure.

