Screen Failure	
A subject who signs an ICF but does not meet clinical eligibility criteria is considered a screen failure. Screen failure subjects do not count towards the enrollment ceiling and will not be used for the primary analyses. Screen failure subjects should exit from the study immediately upon determining ineligibility. The original signed ICF must be maintained in the center's subject file and the following forms must be completed for all information collected prior to determining the subject's ineligibility.
 
• Baseline forms such as, but not limited to, ICF, baseline information and other related forms• Adverse Event form(s) for any reportable event, as defined in Section 17, for any adverse event that occurs after signing the ICF, up to the point of subject exit
Attempt	
A subject who signs an ICF, meets eligibility criteria, and has had a WATCHMAN Access Sheath inserted to implant the device, but eventually does not receive a WATCHMAN FLX device will be classified as "Attempt." Attempt subjects will be followed for 12 months from the time of the implant attempt and adverse events will be collected. Attempt subjects count towards the enrolment ceiling and will be used for analyses of the endpoints. The original signed ICF must be maintained in the centre's study file and the following forms must be completed.
 
• eCRFs in the Baseline and Implant folders• First Follow-up Visit Form(s), except LAA imaging• Adverse Event forms and/or Device Deficiency forms for any reportable adverse event that occurs after signing the ICF• End of Study form for withdrawal 
The date of withdrawal should be indicated in the End of Study form as the point of subject withdrawal.

Implant	A subject who is successfully implanted with the WATCHMAN FLX device will be classified as "Implant." Successfully implanted subjects are those defined as having device success, where the device has been deployed and implanted in the correct position. These subjects are followed in accordance with the follow-up schedule and data will be

Table 9.5-1: Subject Status and Classification

Classification	Description
	included in all study analyses. All applicable case report forms per the protocol must be completed. The original signed ICF and any relevant documentation must be maintained in the centre's study file.

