 - Either CT or TEE assessment of the LAA must be carried out within 14 days prior to the index procedure to confirm LAA size and to document that eligibility criteria have been met. Results must be sent to the core lab. This preprocedural imaging assesses appendage anatomy and device sizing and excludes the presence of a LAA thrombus. Suitability for attempted device implantation will be assessed as follows.
 - Using multiple imaging planes, LAA size/shape, number of lobes in the LAA, and location of lobes to ostium will be determined.

- Absence of thrombus will be confirmed. If an intracardiac thrombus is visualized, device implantation will not be attempted. Re-assessment may be scheduled per the physician's discretion.
- Measurements of the LAA ostium width and LAA depth will be recorded. The measured maximum LAA ostium width must be ≥ 14.0 mm and ≤ 31.5 mm to accommodate the available WATCHMAN FLX device sizes.
- Cardiac MRI assessment (including 4D cardiac MRI flow analysis of the LA and LAA) is optional but if performed, the results must be sent to the core lab.
- All protocol required pre-procedural imaging will be performed by trained individuals and in accordance with core lab instructions (see Section 12.3). Copies of the imaging results will be sent to the core lab for independent analysis. Additionally, copies of all LAA imaging will be saved to disk at the center and available to the sponsor upon request. The center and subject identification number should be clearly identified on the disks.

10.5. *Pre-procedure Medications*

Pre-procedure medications are listed below and should be recorded on the eCRFs.

- Single antiplatelet therapy (aspirin or P2Y₁₂ inhibitor) is recommended prior to device implantation. A loading dose should be administered the day before the implant procedure. Dosing should be per standard of care. The choice of loading dose medication is at the discretion of the treating physician but should be the same as the intended post-procedure antiplatelet therapy.
- Anticoagulant therapy (e.g., unfractionated heparin) must be administered per local standard of care during the implant procedure, with a recommended target activated clotting time (ACT) of ≥ 250 seconds during the implantation procedure.
- Prophylactic antibiotic therapy should be given according to local practice. The choice of antibiotic drug is left to the investigator's discretion.

10.6. *Index Procedure*

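### The screen-failure class has no cut-off at the start of the procedure, so it takes in ineligible failed attempts, overlaps the Implant class and conflicts with the 12-month rules for all enrolled subjects

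*Protocol*

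**What the plan says.** **Definition.** Section 9.1: "A subject who is determined to not meet study specific clinical eligibility criteria after signing consent will be considered a screen failure". Table 9.5-1, Screen Failure row: "A subject who signs an ICF but does not meet clinical eligibility criteria is considered a screen failure". Both start the class at consent. Neither ends it at the procedure.

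**Consequences in the Screen Failure row.** On counting and analysis, the row states: "Screen failure subjects do not count towards the enrollment ceiling and will not be used for the primary analyses". On leaving the study, it adds: "Screen failure subjects should exit from the study immediately upon determining ineligibility". Adverse event forms are required "for any adverse event that occurs after signing the ICF, up to the point of subject exit".

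**Attempt row.** The class is for "A subject who signs an ICF, meets eligibility criteria, and has had a WATCHMAN Access Sheath inserted to implant the device" and who then receives no device. It carries 12 months of follow-up, a place under the ceiling and use in the endpoint analyses.

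**Implant row.** "A subject who is successfully implanted with the WATCHMAN FLX device will be classified as" Implant. Eligibility is not a condition. The row requires scheduled follow-up and puts the data in all analyses.

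**Elsewhere.** Section 9.1 makes the signed consent form the point of enrollment. Section 7.3 promises safety and effectiveness results on all enrolled subjects. Section 10.9 follows all of them for 12 months, and Section 17.1 has reportable events collected to 12 months for all of them. Table 10.1-1 (footnote a) and Section 10.8 keep enrolled subjects without a correctly placed device in safety follow-up to 12 months. Section 11.2.1 defines the ITT set by consent and enrollment. None of these makes an exception for screen failures. The synopsis and Section 7.1 set the ceiling at 25 subjects with an attempted placement.

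**The concern.** Ineligibility can come to light after the procedure, and the protocol leaves several routes open:

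- Pre-procedure images serve "to document that eligibility criteria have been met. Results must be sent to the core lab" (Section 10.4), but nothing requires the core laboratory's reading to come before the implant.
- Baseline creatinine may date from up to 180 days before consent (Section 10.4), while EC2 is an eGFR limit.
- EC5 covers procedures planned up to 60 days after implant.
- Monitors review source documents while the study runs (Sections 15 and 19.1).

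If the Screen Failure row is applied at that stage, it acts as an exclusion after treatment, at a time when complications or follow-up images may already be known. A subject exposed to the procedure could leave safety follow-up, and the place would be treated as unused. An analysis plan cannot repair this, because data not collected after exit do not exist.

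**Working it through.** The protocol states no figure to reproduce. The check is a comparison of the rules, followed by an illustration of scale.

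**Case A: sheath inserted, no device implanted, ineligibility found afterwards.**

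- Attempt row: not met, because eligibility is a condition.
- Implant row: not met, because there is no device.
- Screen Failure row: met (consent signed, eligibility not met).
- Result within the table: should exit at once, events recorded only to exit, no place used under the ceiling.
- Against this: Table 10.1-1 footnote a and Sections 10.8, 10.9 and 17.1 require safety follow-up and reporting to 12 months. Section 11.2.1 keeps the subject in ITT. Section 7.1 counts the attempt towards the 25.

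**Case B: device implanted in the correct position, ineligibility found afterwards.**

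- Screen Failure row: met. The subject should exit and is not used for the primary analyses.
- Implant row: also met. The subject is followed on schedule and included in all analyses.
- No rule says which row takes precedence. Sections 7.3, 10.9, 11.2.1 and 17.1 agree with the Implant row.

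**Could a screen failure count as not enrolled?** Section 9.1 enrolls at signature and nothing reverses that. Section 11.2.2 describes enrollment as consent plus selection to receive a device, which a treated subject also satisfies. Under either wording the rules for enrolled subjects apply in both cases.

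**Illustration of scale.** Maximum N = 25 (Section 11.2.3), so one subject is 1/25 = 4.0%. Suppose the only subject with a given event is reclassified and leaves the denominator. Exact (Clopper-Pearson) 95% limits:

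- Before, 1/25 = 4.0%. Lower limit 1 − 0.975^(1/25) = 0.1%. Upper limit, the 97.5% point of Beta(2, 24), = 20.4%.
- After, 0/24 = 0%. Upper limit 1 − 0.025^(1/24) = 14.2%.

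The frequency is unknown. If each subject has an assumed chance q of ineligibility found late, the chance of at least one case among 25 is 1 − (1 − q)^25:

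| Assumed q | At least one in 25 |
|---|---|
| 2% | 40% |
| 5% | 72% |
| 10% | 93% |

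The protocol supports none of these values of q over another.

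**The case against.** The strongest reply is that a pre-procedure class was plainly meant. Eligibility is confirmed at baseline (Section 10.4, Table 10.1-1). The forms named for screen failures are baseline and adverse event forms, and the Implant-folder and device deficiency forms first appear in the Attempt row. That is probably the intention, but no sentence says so, and the Attempt row's eligibility condition works against it.

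A reader might infer that every treated subject found ineligible must leave the study and be lost to the primary analyses. The documents do not support that, for these reasons:

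- The wording is should, not must.
- For an implanted subject the Implant row independently requires follow-up and inclusion.
- A failed attempt has no follow-up imaging (Section 10.8) and so never contributes to the primary endpoint of device surface morphology. What is at stake there is safety follow-up and the additional endpoints.
- The stated exclusion names only the primary analyses, and clinical events are additional endpoints (Section 6.2). Events are lost because collection ends at exit.
- Events before exit are still recorded. Section 9.4 has open events assessed at withdrawal, and device-related events followed to resolution where possible and with consent.

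One discovery route is also thin. The numbered criteria contain no appendage-width or thrombus limit, which are the main imaging checks in Section 10.4. Selective triggering after a complication is possible, but nothing in the protocol shows it. The study is descriptive, so no test or error rate is affected.

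These points narrow the consequence. They do not remove the defect: the sections that protect treated subjects contradict Table 9.5-1 and do not override it.

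**Conclusion.** The point holds as an internal contradiction with a real safety-data consequence. The screen-failure class lacks a cut-off at the start of the index procedure. An ineligible failed attempt therefore falls only into that class, and an implanted subject found ineligible falls into two classes with opposite instructions. Both outcomes conflict with the 12-month follow-up, reporting and ITT rules for enrolled subjects, and with a ceiling defined by attempted placement.

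The size is up to 12 months of safety follow-up per affected subject, each being 4% of the maximum sample. The 1/25 against 0/24 comparison and the probabilities of at least one case are illustrations only, because they rest on an assumed event and assumed rates. The conclusion rests on the wording alone and assumes no separate instruction to the site sets a cut-off. It does not extend to ordinary screen failures found before the procedure, or to a claim that the protocol compels the removal of treated subjects. It is worth correcting because the cost is small and uncollected follow-up cannot be recovered.

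**What to change.** In Section 9.1 and Table 9.5-1:

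1. Limit screen failure to ineligibility determined before the index procedure starts. Define that start by one event that joins up with the sheath insertion used in the Attempt row, so that no subject falls between classes.
2. Delete the eligibility condition from the Attempt row.
3. State that ineligibility found later is recorded as a deviation under Section 13. The subject keeps the Attempt or Implant class, counts towards the 25, stays in 12-month safety follow-up, and stays in the analyses with whatever data are collected.

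The change should not mandate the imaging schedule. Some criteria bear on the tests themselves: EC2 concerns kidney function, EC3 concerns TEE, and Section 16.2 warns about contrast. Whether protocol CT or TEE continues in a subject found ineligible on such a criterion is a clinical matter that the sponsor must reconcile in the text.

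The cost is a few sentences of protocol wording. No extra subjects are needed, and the safety follow-up is what Sections 10.8, 10.9 and 17.1 already require.
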